5. ASSESSMENT OF SAFETY

5.1 SAFETY PLAN

The safety profile of alteplase across indications is generally well established. The principal adverse reactions to alteplase are bleeding and allergic reactions.

Alteplase—Genentech, Inc.
45/Protocol ML29093, Version 3

5.1.1 Risk of Bleeding

Bleeding is the most frequent adverse reaction associated with alteplase in all approved indications, including AIS. This may be either superficial from punctures or damaged blood vessels or internal bleeding at any site or body cavity. Bleeding may result in life-threatening situations, permanent disability, or death.

- The incidence of ICH, especially symptomatic ICH, in patients with AIS is higher in alteplase-treated patients than placebo-treated patients in published studies (for detailed information, see the alteplase USPI).

Management of Bleeding

Patients will be excluded for the presence of conditions related to risks of bleeding (as outlined in Section 4.1.2, Exclusion Criteria). A non-contrast cranial CT or MRI (including either SW or GRE to detect ICH) should be performed at baseline to ensure that the patient does not have evidence of ICH prior to study drug administration.

Fibrin, which is part of the hemostatic plug formed at needle puncture sites, may be lysed during alteplase therapy. Therefore, alteplase therapy requires careful attention to potential bleeding sites, e.g., catheter-insertion sites and arterial-puncture sites. Arterial and venous punctures should be minimized. Non-compressible arterial, as well as internal jugular and subclavian venous punctures, should be avoided to minimize bleeding from non-compressible sites. In the event of serious bleeding (not controllable by local pressure) or occurring in a critical location (intracranial, gastrointestinal, retroperitoneal, or pericardial), study drug should be discontinued immediately.

Supportive care and medical management of AEs are at the discretion of the investigator.

5.1.2 Risk of Allergic Reactions

Allergic-type reactions, e.g., anaphylactoid reaction, laryngeal edema, orolingual angioedema, rash, and urticaria, have been reported. When such reactions occur, they usually respond to conventional therapy.

There have been postmarketing reports of orolingual angioedema associated with the use of alteplase. Most were patients treated for AIS. Many of these patients received concomitant angiotensin-converting enzyme inhibitors, and most cases resolved with prompt treatment.

Management of Allergic Reaction

If an anaphylactic reaction occurs, the infusion of study drug should be discontinued immediately and appropriate therapy should be promptly instituted.

5.2 SAFETY PARAMETERS AND DEFINITIONS

Safety assessments will consist of monitoring and recording AEs, including SAEs and non-serious adverse events of special interest (AESIs), *performing protocol-specified safety laboratory assessments, performing protocol-specified vital signs, and conducting*

Alteplase—Genentech, Inc.
46/Protocol ML29093, Version 3

other protocol-specified tests that are deemed critical to the safety evaluation of the study.

Certain types of events require immediate reporting to the Sponsor, as outlined in Sections [5.2.2](#) and [5.2.3](#).

5.2.1 Adverse Events

According to the International Conference on Harmonisation guideline for Good Clinical Practice, an AE is any untoward medical occurrence in a clinical investigation patient administered a pharmaceutical product, regardless of causal attribution. An AE can therefore be any of the following:

- Any unfavorable and unintended sign (including an abnormal laboratory finding), symptom, or disease temporally associated with the use of a medicinal product, whether or not considered related to the medicinal product
- Any new disease or exacerbation of an existing disease (a worsening in the character, frequency, or severity of a known condition), except as described in Section [5.3.3.9](#)
- Recurrence of an intermittent medical condition (e.g., headache) not present at baseline
- Any deterioration in a laboratory value or other clinical test (e.g., electrocardiogram, X-ray) that is associated with symptoms or leads to a change in study treatment or concomitant treatment or discontinuation from study drug

5.2.2 Serious Adverse Events (Immediately Reportable to the Sponsor)

An SAE is any AE that meets any of the following criteria:

- Is fatal (i.e., the AE actually causes or leads to death)
- Is life-threatening (i.e., the AE, in the view of the investigator, places the patient at immediate risk of death)

This does not include any AE that, had it occurred in a more severe form or was allowed to continue, might have caused death.

- Requires or prolongs inpatient hospitalization (see Section [5.3.3.9](#))
- Results in persistent or significant disability/incapacity (i.e., the AE results in substantial disruption of the patient's ability to conduct normal life functions)
- Is a congenital anomaly/birth defect in a neonate/infant born to a mother exposed to study drug
- Is a significant medical event in the investigator's judgment (e.g., may jeopardize the patient or may require medical/surgical intervention to prevent one of the outcomes listed above)

The terms "severe" and "serious" are not synonymous. Severity refers to the intensity of an adverse event (rated as mild, moderate, or severe); the event itself may be of

relatively minor medical significance (such as severe headache). “Serious” is a regulatory definition and is based on patient or event outcome or action criteria usually associated with events that pose a threat to a patient’s life or vital functions. Seriousness (not severity) serves as the guide for defining regulatory reporting obligations.

Severity and seriousness need to be independently assessed for each AE recorded on the eCRF.

SAEs are required to be reported by the investigator to the Sponsor immediately (i.e., no more than 24 hours after learning of the event; see Section [5.4](#) for reporting instructions).

5.2.3 Non-Serious Adverse Events of Special Interest (Immediately Reportable to the Sponsor)

Non-serious AESIs are required to be reported by the investigator to the Sponsor immediately (i.e., no more than 24 hours after learning of the event; see Section [5.4.1](#) for reporting instructions). AESIs for this study include the following:

- sICH events, if not already reported as an SAE (for a list of preferred terms for ICH see [Appendix 13](#))
- Stroke recurrence: report if the AE resulted in a substantial disruption of a person’s ability to conduct normal life functions (i.e., the AE resulted in a significant, persistent, or permanent change; impairment; or damage or disruption in the patient’s body function/structure, physical activities, and/or quality of life).
- In addition, Suspected Transmission of an Infectious Agent via a Medicinal Product (STIAMP) by the study drug in a Genentech-sponsored trial qualifies as an AESI and requires immediate reporting to the Sponsor.

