3.5.3 Exploratory Outcome Measures

The exploratory outcome measures for this study are as follows:

- NIHSS at Day 90
- Instrumental activities of daily living, as measured by the BI at Day 90
- GOS at Day 90
- Stroke recurrence (based on AE monitoring) within 90 days
- Cognition and behavior (modified 30-minute battery: Controlled Oral Word Association test; Hopkins Verbal Learning Test-Revised [HVLT-R] trials 1, 2, and 3; digit symbol coding from the Wechsler Adult Intelligence Scale III [WAIS III]; Forward and Backward Digit Span test; Benton Judgment of Line Orientation test, form V; HVLT-R trial 4 and recognition; semantic fluency [Animal Naming test]; Boston Naming Test [BNT 15-item short form]) at Day 90
- Ambulatory performance (as measured by walking speed) at Day 90
- Depression (CES-D score) at Day 90
- Quality of life (EQ-5D questionnaire) at Day 90
- SIS-16 at Day 90

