5.3.1 Adverse Event Reporting Period

Investigators will seek information on AEs at each patient contact. All AEs, whether reported by the patient or noted by study personnel, will be recorded in the patient’s medical record and on the Adverse Event eCRF.

After initiation of study drug, all AEs (including serious and non-serious AEs), regardless of relationship to study drug, will be reported until 30 days after administration of study drug.

After 30 days until 90 days after administration of study drug, the following AEs should be recorded on the AE CRF:

- All SAEs
- Non-serious ICHs
- Non-serious AESIs
- All AEs that resulted in withdrawal from the study

All SAEs and non-serious AESIs require immediate reporting to the Sponsor (see Section 5.4).

After 90 days, the investigator is not required to actively monitor patients for AEs; however, the Sponsor should be notified if the investigator becomes aware of any post-study SAEs (see Section 5.6).

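### The 90-day stroke recurrence endpoint has no seriousness qualifier, but after Day 30 the protocol does not reliably collect mild, non-serious ischemic recurrences

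*Protocol*

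**What the plan says.** Sections 2.3 and 3.5.3 name the endpoint in the same words: "Stroke recurrence (based on AE monitoring) within 90 days". Neither restricts it by severity or seriousness, and adverse event monitoring is its only stated data source.

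Section 5.3.1 sets two collection periods. In the first, all events, serious or not, "will be reported until 30 days after administration of study drug". In the second, the rule reads "After 30 days until 90 days after administration of study drug, the following AEs should be recorded on the AE CRF", followed by four categories: SAEs, "Non-serious ICHs", "Non-serious AESIs" and "All AEs that resulted in withdrawal from the study". Section 4.6.5 applies the same restricted set at the Day 90 visit, and Section 5.6 gives the reporting period for non-serious events as 30 days.

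Section 5.2.3 includes recurrence among the non-serious AESIs, with a condition: "Stroke recurrence: report if the AE resulted in a substantial disruption of a" person's capacity for normal life functions. A parenthesis then explains that condition by reference to change, impairment, damage or disruption in body function, physical activity or quality of life. The SAE criterion in Section 5.2.2 is: "Results in persistent or significant disability/incapacity (i.e., the AE results in" a substantial disruption of those same functions.

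**The concern.** The endpoint depends entirely on what sites record as adverse events, and the recording rule narrows at Day 30 while the endpoint definition does not. Recurrence appears in the AESI list, which looks like the device meant to carry it across Day 30. If its condition is met only by events that are already serious, it does not do that job.

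At stake is what the reported rate means. A figure presented as recurrence within 90 days would in fact be any recurrence to Day 30 plus essentially serious recurrence from Day 30 to Day 90. A statistical analysis plan cannot repair this later, because the events would not be in the database.

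**Working it through.** The protocol gives no recurrence rate or expected count, so there is no figure to reproduce. The check is to trace each kind of recurrence after Day 30 through the collection rules of Version 3.

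1. **Hospitalized, life-threatening or fatal recurrence.** An SAE under 5.2.2, recorded to Day 90.
2. **Disabling recurrence.** An SAE under the disability criterion of 5.2.2. It also meets the AESI condition of 5.2.3, but that adds nothing because it is already recorded.
3. **Neither hospitalized nor disabling, but judged a significant medical event by the investigator.** An SAE under the last criterion of 5.2.2, recorded.
4. **Non-serious hemorrhagic stroke.** Recorded as a non-serious ICH; hemorrhagic stroke is on the term list in Appendix 13.
5. **Recurrence that leads to withdrawal from the study.** Recorded.
6. **Mild ischemic recurrence with none of these features.** The only listed route left is the recurrence AESI. Its lead condition uses the same test as the SAE disability criterion, so on that reading an event that qualifies is already serious and one that is not serious does not qualify. Only a broad reading of the parenthesis in 5.2.3 would bring it in.

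Could another Day 90 form supply the missing events? The first NIHSS item in Appendix 7 asks about stroke, but it combines the index stroke with any outcome stroke, so it cannot identify a recurrence.

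The restricted rule covers 90 − 30 = 60 days, and 60/90 = 67% of the endpoint window.

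The size of the loss can only be illustrated. Let s be the share of recurrences that are non-serious with no other route, and t the share that occur after Day 30, taken as independent. The unrecorded share is s × t. Neither value is in the protocol; the ranges here are assumptions:

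- Low: s = 0.10, t = 0.20, giving 0.10 × 0.20 = 0.02, or 2%.
- High: s = 0.40, t = 0.67 (recurrences spread evenly over the 90 days), giving 0.40 × 0.67 = 0.27, or 27%.
- If every recurrence is judged serious, s = 0 and the loss is 0%.

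**The case against.** A reader might infer that the endpoint cannot be measured, that the recurrence AESI is an empty category, or that a non-hospitalized, non-disabling recurrence after Day 30 is never recorded. The text does not support these absolutes:

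- The parenthesis in 5.2.3 is wider than anything in 5.2.2. An investigator could read a new deficit as an impairment that satisfies it.
- The significant-medical-event criterion in 5.2.2 needs neither admission nor disability, and a new stroke soon after the index stroke is an obvious candidate.
- The opening paragraph of 5.3.1 says, without a time limit, that all adverse events go on the eCRF and that sites ask about events at every contact.
- Section 5.3.3.8 requires unexpected worsening of the index stroke to be recorded throughout the study and resolves doubt in favor of reporting.

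The shorter period is also a reasoned choice. The Version 2 amendment explains it as alignment with other acute stroke studies and a lighter Day 90 visit, intended to limit missing data. The same amendment added the recurrence AESI.

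Much of this stands, and it limits the claim to unreliable capture. It does not remove the problem. The opening sentence of 5.3.1 conflicts with the specific list below it and with 5.6, so sites cannot follow both. Section 5.3.3.8 concerns worsening of the index stroke and does not name recurrence. The remaining routes depend on how an investigator classes a mild event, which is not a collection rule. The reason for shortening general collection does not require a qualifier on this one event: non-serious ICHs stay on the Day 30–90 list without one.

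**Conclusion.** The mismatch is real and confined to one exploratory outcome. To Day 30 any recurrence counts. From Day 30 to Day 90 the recurrences assured of collection are the serious ones, plus non-serious hemorrhagic events and those causing withdrawal. A mild, non-hospitalized ischemic recurrence in that period that the investigator does not judge medically significant is not reliably collected, so the 90-day rate can be understated.

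The number missed cannot be obtained from the protocol. The 2% to 27% range rests wholly on assumed values, and zero is possible. A reader might also infer a bias between alteplase and aspirin, but the same rule applies to both blinded arms and the protocol shows no directional effect. Nor does it establish that mild recurrences are the commonest kind. The primary and secondary analyses, the sample size and the named hemorrhage and mortality outcomes are untouched. This is a cheap improvement worth making, not a threat to the trial's conclusions.

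**What to change.** Make one of two edits: remove the disruption condition from the recurrence bullet in 5.2.3, so that any recurrent stroke is an AESI to Day 90; or add all recurrent strokes, serious or not, to the Day 30–90 list in 5.3.1. With either, reconcile the opening all-events sentence of 5.3.1 with that list.

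If the sponsor prefers to leave collection as it is, restate the endpoint in 2.3 and 3.5.3 as any recurrence to Day 30 and serious recurrence to Day 90.

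The cost is one bullet, one reconciling sentence and a few more AE or AESI reports. Under the first option those reports would carry the 24-hour reporting duty that applies to AESIs.

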5.3 METHODS AND TIMING FOR CAPTURING AND ASSESSING SAFETY PARAMETERS

The investigator is responsible for ensuring that all AEs (see Section [5.2.1](#) for definition) are recorded on the Adverse Event eCRF and reported to the Sponsor in accordance with instructions provided in this section and in Sections [5.4–5.6](#).

For each AE recorded on the Adverse Event eCRF, the investigator will make an assessment of seriousness (see Section [5.2.2](#) for seriousness criteria), severity (see Section [5.3.2](#)), and causality (see Section [5.3.3](#)).

5.3.1 Adverse Event Reporting Period

Investigators will seek information on AEs at each patient contact. All AEs, whether reported by the patient or noted by study personnel, will be recorded in the patient’s medical record and on the Adverse Event eCRF.

After initiation of study drug, all AEs (including serious and non-serious AEs), regardless of relationship to study drug, will be reported until 30 days after administration of study drug.

After 30 days until 90 days after administration of study drug, the following AEs should be recorded on the AE CRF:

- All SAEs
- Non-serious ICHs
- Non-serious AESIs
- All AEs that resulted in withdrawal from the study

All SAEs and non-serious AESIs require immediate reporting to the Sponsor (see Section 5.4).

After 90 days, the investigator is not required to actively monitor patients for AEs; however, the Sponsor should be notified if the investigator becomes aware of any post-study SAEs (see Section 5.6).

5.3.2 Assessment of Severity of Adverse Events

The WHO toxicity grading scale (see [Appendix 14](#)) will be used for assessing adverse event severity. Table 4 will be used for assessing severity for adverse events that are not specifically listed in the WHO toxicity grading scale.

Table 4 Adverse Event Severity Grading Scale

Grade	Severity
1	Mild; transient or mild discomfort (<48 hours); no medical intervention or therapy required
2	Moderate; mild to moderate limitation in activity; some assistance may be needed; no or minimal medical intervention or therapy required
3	Severe; marked limitation in activity; some assistance usually required; medical intervention or therapy required; hospitalization possible
4	Life-threatening; extreme limitation in activity; significant assistance required; significant medical intervention or therapy required, hospitalization or hospice care probable

Notes: Developed by the Division of Microbiology and Infectious Diseases.

Regardless of severity, some events may also meet seriousness criteria. Refer to definition of a serious adverse event (see Section 5.2.2).

5.3.3 Assessment of Causality of Adverse Events

Investigators should use their knowledge of the patient, the circumstances surrounding the event, and an evaluation of any potential alternative causes to determine whether or not an AE is considered to be related to the study drug, indicating "yes" or "no" accordingly. The following guidance should be taken into consideration (see also [Table 5](#)):

- Temporal relationship of event onset to the initiation of study drug
- Course of the event, considering especially the effects of dose reduction, discontinuation of study drug, or reintroduction of study drug (as applicable)
- Known association of the event with the study drug or with similar treatments
- Known association of the event with the disease under study
- Presence of risk factors in the patient or use of concomitant medications known to increase the occurrence of the event
- Presence of non-treatment-related factors that are known to be associated with the occurrence of the event

Table 5 Causal Attribution Guidance

Is the adverse event suspected to be caused by the study drug on the basis of facts, evidence, science-based rationales, and clinical judgment?	
YES	There is a plausible temporal relationship between the onset of the adverse event and administration of the study drug, and the adverse event cannot be readily explained by the patient's clinical state, intercurrent illness, or concomitant therapies; and/or the adverse event follows a known pattern of response to the study drug; and/or the adverse event abates or resolves upon discontinuation of the study drug or dose reduction and, if applicable, reappears upon re-challenge.
NO	Adverse events will be considered related, unless they fulfill the criteria as specified below. Evidence exists that the adverse event has an etiology other than the study drug (e.g., preexisting medical condition, underlying disease, intercurrent illness, or concomitant medication); and/or the adverse event has no plausible temporal relationship to administration of the study drug (e.g., cancer diagnosed 2 days after first dose of study drug).

5.3.3.1 **Diagnosis versus Signs and Symptoms**

A diagnosis (if known) should be recorded on the Adverse Event eCRF rather than individual signs and symptoms (e.g., record only liver failure or hepatitis rather than jaundice, asterixis, and elevated transaminases). However, if a constellation of signs and/or symptoms cannot be medically characterized as a single diagnosis or syndrome at the time of reporting, each individual event should be recorded on the Adverse Event eCRF. If a diagnosis is subsequently established, all previously reported AEs based on signs and symptoms should be nullified and replaced by one AE report based on the single diagnosis, with a starting date that corresponds to the starting date of the first symptom of the eventual diagnosis.

Alteplase—Genentech, Inc.
50/Protocol ML29093, Version 3

5.3.3.2 Adverse Events Occurring Secondary to Other Events

In general, AEs occurring secondary to other events (e.g., cascade events or clinical sequelae) should be identified by their primary cause, with the exception of severe or serious secondary events. However, medically significant AEs occurring secondary to an initiating event that are separated in time should be recorded as independent events on the Adverse Event eCRF. For example:

- If vomiting results in mild dehydration with no additional treatment in a healthy adult, only vomiting should be reported on the eCRF.
- If vomiting results in severe dehydration, both events should be reported separately on the eCRF.
- If a severe gastrointestinal hemorrhage leads to renal failure, both events should be reported separately on the eCRF.
- If dizziness leads to a fall and consequent fracture, all three events should be reported separately on the eCRF.
- If neutropenia is accompanied by an infection, both events should be reported separately on the eCRF.

All AEs should be recorded separately on the Adverse Event eCRF if it is unclear as to whether the events are associated.

5.3.3.3 Persistent or Recurrent Adverse Events

A persistent AE is one that extends continuously, without resolution, between patient evaluation timepoints. Such events should only be recorded once on the Adverse Event eCRF. The initial severity (*intensity or grade*) of the event should be recorded *at the time the event is first reported*. *If a persistent AE becomes more severe, the most extreme severity should also be recorded on the Adverse Event eCRF. If the event becomes serious, it should be reported to the Sponsor immediately (i.e., no more than 24 hours after learning that the event became serious; see Section 5.4.1 for reporting instructions). The Adverse Event eCRF should be updated by changing the event from "non-serious" to "serious," providing the date that the event became serious, and completing all data fields related to SAEs.*

A recurrent AE is one that resolves between patient evaluation timepoints and subsequently recurs. Each recurrence of an AE should be recorded *as a separate event* on the Adverse Event eCRF.

